1.0 LIST OF ABBREVIATIONS

AE: Adverse Event

AES-S: Apathy evaluation scale

CBGD: Corticobasal ganglionic degeneration

CBS: Corticobasal Syndrome DBS: Deep Brain Stimulators

ET: Essential tremor

FAB: Frontal Assessment Battery

FOG: Freezing of gait

FOG-Q: Freezing of gait questionnaire MoCA: Montreal cognitive assessment

MSA: Multiple systems atrophy

PAGF: Primary akinesia with gait freezing

PD: Parkinson's disease

PDQ-39: Parkinson's disease questionnaire for quality of life

PKMAS: Protokinetic movement analysis software

PPFG: Primary progressive freezing of gait

PPN: Pedunculopontine nucleus PSP: Progressive supranuclear palsy

RBD: Rapid eye movement sleep behavior disorder

SCOPA-COG: Scales for outcome in Parkinson's disease - cognition

SSRIs: selective serotonin reuptake inhibitors

SWS: stand-walk-sit

TCAs: tricyclic antidepressants

UPDRS: Unified Parkinson's Disease Rating Scale

Study Title: Modafinil for FOG (UAMS IRB#206341) PI: [name], PhD Sponsor: UAMS

2.0 STUDY SUMMARY

Title	Modafinil as a novel therapy for the treatment of freezing of gait in Parkinson's disease			
Short Title	Modafinil for FOG			
Protocol Number	MODFOG01			
Phase	Pilot, feasibility			
Methodology	Randomized, placebo-controlled delayed start			
Study Duration	1 year			
Study Center(s)	Single-center			
Objectives	Safety and efficacy of Modafinil for the treatment of freezing of gait in Parkinson's disease			
Number of Subjects	Enrolling 25 for a total of 20			
Diagnosis and Main Inclusion Criteria	Idiopathic Parkinson disease with freezing of gait on stable Parkinson disease treatment for 3 months.			
Study Product(s), Dose, Route, Regimen	Modafinil 50 mg capsule oral daily, Placebo capsule oral daily			
Duration of administration	24 weeks (early-start), 12 weeks (delayed-start)			
Reference therapy	none			
Statistical Methodology	The study is a prospective repeated measures longitudinal design. A primary statistical goal is to estimate the mean response at all six time points for each group and subsequently estimate changes in the outcome measures for each study group from baseline.			

PI: [name], PhD

Sponsor: UAMS

3.0 BACKGROUND AND RATIONALE

3.1 Disease Background

Patients with Parkinson Disease (PD) typically present with bradykinesia, rigidity, and frequently resting tremor along with other hallmarks such as shuffling gait, decreased blinking, decreased arm swing, hypophonia, hypomimia, micrographia, and decreased smell and taste. In the later stages of the disease, dementia, postural instability, and freezing of gait are also common. Freezing of gait (FOG) is one of the more debilitating motor complications of PD.^{1, 2} It is manifested by the feet "sticking to the ground" for several seconds during active movement. FOG occurs initially when the patient is turning or when initiating gait (start-hesitation). Later, it occurs when the patient reaches a destination, such as a chair, and the patient stops too soon, before fully reaching the desired destination.

FOG is a complex disorder that can also be seen as an entity of its own in primary progressive freezing of gait (PPFG), primary akinesia with gait freezing (PAGF), or in atypical Parkinsonism such as vascular Parkinsonism, progressive supranuclear palsy (PSP), corticobasal syndrome (CBS), and multiple systems atrophy (MSA). FOG has been thought to be due either to a variant in the disease process in certain individuals, or potentially as a side effect of levodopa, one of the mainstay medications used to treat the symptoms of PD. Earlier onset FOG has been associated with earlier onset of dyskinesias and postural instability, the presence of hallucinations and greater neocortical Lewy Body burden.³ FOG in PD can occur both as a phenomenon of the "OFF state" which improves with addition of dopaminergic medications (i.e., either levodopa or dopamine agonists), but in an unknown percentage it also occurs in the "ON state" and does not respond to increased levodopa. In fact FOG in the "ON state" is often reported to worsen with incrementally higher levodopa doses.

The presence of gait freezing results in a significant worsening of quality of life for patients. Freezing leads to decreased mobility, increased rates of falls, and subsequent fear of falling, which further limits mobility. Morbidity associated with hip fractures from falls leads to hospitalizations, surgeries and further dependence on caregivers. Often, patients lapse into a wheelchair- or home-bound state, increasing pressure on care givers. While OFF state FOG usually responds to increases in levodopa dosing, ON state FOG does not, and can even worsen.

Unfortunately, no good alternative treatments exist for FOG. Methylphenidate, a stimulant used in the treatment of Attention deficit hyperactivity disorder, inhibits presynaptic dopamine⁸ and the noradrenaline transporter. Used at high doses (1 mg/kg/day), methylphenidate has been shown to decrease the number of steps taken by PD patients who have undergone subthalamic nucleus (STN) DBS in the stand-walk-sit (SWS) test, but it has not been widely adopted due to cardiac side effects.⁹ Therefore, we will test whether another stimulant, Modafinil, could serve as a novel treatment for FOG.

3.2 Investigational Product Background

The pedunculopontine nucleus (PPN) is a part of the reticular activating system, and arousing stimuli simultaneously activate ascending projections to the intralaminar thalamus triggering high frequency cortical activity, and descending projections to the reticulospinal systems altering posture and locomotion. This has led to the PPN being

PI: [name], PhD

Sponsor: UAMS

used as a target for deep brain stimulation (DBS) in the treatment of PD, and proposed as a potential target for treating FOG in PD.¹⁰⁻¹² PPN neurons fire at beta/gamma frequencies during waking and REM sleep but not during slow wave sleep.¹³ These oscillations are mediated by high threshold voltage dependent N- and P/Q-type calcium channels.¹⁴ [name] and colleagues have shown that beta/gamma oscillations in PPN neurons were blocked by KN-93 (a CAMKII activation inhibitor), which suggests that at least some cells produce oscillations through the CAMKII pathway.

Modafinil, a stimulant approved by the FDA for treatment of narcolepsy (decreases daytime sleepiness and regulates sleep-wake cycles), has a number of putative sites of action. ¹⁵ [name] and colleagues, as well as a group of researchers at NYU have both shown that modafinil works by increasing neuronal electrical coupling, and this action of modafinil is also modulated by the CAMKII pathway as KN-93 also inhibits the effects of modafinil. ^{16, 17} Modafinil has also been shown to bind to the dopamine transporter and prevent dopamine reuptake, increasing the level of dopamine in the synaptic cleft. ¹⁸

Modafinil is a 1:1 racemic compound whose enantiomers have different pharmacokinetics (The half-life of R-modafinil is approximately three times that of S-Modafinil in humans). The effective elimination half-life of Modafinil is about 15 hours with linear kinetics upon multiple dosing of 200-600 mg/day with steady state reached after 2-4 days of dosing for narcolepsy. Modafinil is absorbed orally with peak plasma concentrations in 2-4 hours. The major route of elimination is metabolism (approximately 90%) by the liver with subsequent renal elimination of metabolites. In-vitro data suggests that Modafinil is a weak inducer of CYP3A activity in a concentration dependent manner and therefore may reduce the effectiveness of drugs that are substrates for CYP3A enzymes (e.g. steroidal contraceptives, cyclosporine, midazolam, triazolam). Data also suggest that Modafinil is a weak inducer of CYP1A2, CYP2B6, and CYP2C9 (warfarin and phenytoin). Modafinil is also a reversible inhibitor of CYP2C19 and therefore may increase concentrations of drugs metabolized by this enzyme (e.g. phenytoin, diazepam, propranolol, omeprazole, and clomipramine). Modafinil may interact with some CNS active drugs that PD patients may be using including certain tricyclic antidepressants (TCAs) (metabolized by CYP2C19) and selective serotonin uptake inhibitors (SSRIs) (metabolized by CYP2D6). Also concomitant administration of quetiapine reduced the systemic exposure of quetiapine.

Based on data from the [name] lab and a prior unpublished trial at the Little Rock VA on Modafinil in PTSD patients, subjects were found to be more jittery at doses of 100mg and higher (unpublished, personal communication). Therefore for this study low dose Modafinil at 50 mg orally daily will be trialed (the FDA approved recommended dosing for Narcolepsy is 200 mg/day for Narcolepsy). Additionally small studies in elderly populations suggest decreased clearance of Modafinil in elderly populations. One study showed approximately 20% decrease in oral clearance in 12 subjects given a single dose of 200 mg modafinil (mean age 63 years, range 53-72 years), while a study with multiple doses of 300 mg/day Modafinil in 12 subjects (mean age 82 years, range 67-87 years) showed mean plasma levels were two times those in historical younger subjects.

PI: [name], PhD

Sponsor: UAMS

3.3 Rationale

FOG is present in approximately 60% of patients with PD and is a major cause of gait impairment leading to falls, and the morbidity and decreased quality of life. Currently, other than levodopa therapy, which can be limited in later stages of disease when FOG occurs by dose dependent side effects, no alternative treatments exist. Modafinil, as described above, has been shown by the [name] lab to modulate pathways in the PPN that link arousal and gait dynamics. Additionally, PPN DBS has also been shown to modulate gait and falls in patients. As such, we propose to study whether Modafinil can improve FOG in PD. For this pilot study, we will focus on recruiting PD patients with FOG and use a delayed start trial model to determine whether FOG improves compared to placebo. We chose the delayed start trial model as opposed to just having a placebo arm as it will likely help with recruitment and subject retention if all subjects know that at least during 3 months of the trial they will all be receiving active drug. Additionally, preliminary data (unpublished, UAMS IRB#203234) from my lab suggests that PD patients with FOG have a faster rate of decline in objective gait parameters compared to PD patients, even over a period of 3-6 months. Therefore, with the delayed start model we will also determine if there are any changes in the slope of decline in PD-FOG patients over the period of the trial.

4.0 STUDY OBJECTIVES

This is a single-center, prospective, randomized, double-blinded, placebo-controlled, delayed-start pilot trial involving up to 25 subjects with PD and FOG. Subjects will be randomized 1:1 to early start (24 weeks active treatment) or delayed start (12 weeks placebo followed by 12 weeks active treatment) oral Modafinil 50 mg/day. Following 24 weeks of treatment, a 2 week washout of the drug will be performed with a follow-up assessment at 26 weeks.

4.1 Primary Objectives

- **4.1.1** To determine if 50 mg/day Modafinil decreases FOG in PD patients with FOG compared with placebo as measured by the Giladi Freezing of gait questionnaire (FOG-Q).
- **4.1.2** To determine if 50 mg/day Modafinil decreased the decline stride length seen in PD patients with FOG.

4.2 Secondary Objectives

- **4.2.1** To determine if 50 mg/day Modafinil improves motor function in PD patients with FOG compared to placebo as measured by the UPDRS Part III motor subscale.
- **4.2.2** To describe the adverse events associated with Modafinil dosed at 50 mg/day for 3-6 months in PD patients.
- **4.2.3** To determine if quality of life is improved with Modafinil as measured by the PDQ-39.
- **4.2.4** To determine if sleep disorders are improved with Modafinil as measured by the RBD scale and Epworth Sleepiness Scale.

PI: [name], PhD

Sponsor: UAMS

4.3 Exploratory Objectives

4.3.1 To determine if Modafinil 50 mg/day improves cognitive function in PD patients with FOG compared to placebo as measured by the Montreal Cognitive assessment, Stroop test, Frontal Assessment Battery and Scales for Outcome in Parkinson disease, Cognitive assessment (SCOPA-cog)

4.4 Endpoints

4.4.1 Primary Endpoints

- 4.4.1.1 To determine if 50 mg/day Modafinil decreases freezing of gait in PD patients with FOG compared with placebo as measured by the Giladi Freezing of gait questionnaire (FOG-Q) after 12 weeks of active treatment or placebo. Subjects who drop out of the study after at least 6 weeks of either treatment arm will be included in this analysis.
- 4.4.1.2 To determine if 50 mg/day Modafinil decreased the decline stride length seen in PD patients with FOG. The rate of decline in stride length will be compared plotting the stride length at steady state in subjects in the early and late-start arms to determine if the rate of decline improves in subjects taking Modafinil in the early-start arm and whether this rate of decline also improves in the second phase of the trial in the delayed-start arm.

We will also determine if at the completion of 24 weeks, the early-start arm has differential change in slope of other continuous gait parameters (stride width, gait cycle time, gait cycle velocity, swing and stance percent, total single and double support time, cadence) compared to the delayed start arm suggesting that Modafinil slows the progression of the gait decline.

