6.2 Treatment Dosage and Administration

The research pharmacy will create a randomization log, randomizing 20 subjects 1:1 to early start or delayed start modafinil (Figure 1). Subjects will be assigned the next line in the log in order of treatment. Subjects in the early-start arm will receive Modafinil 50 mg oral daily (a.m.) for 24 weeks while subjects in the delayed-start arm will receive oral placebo for the first 12 weeks of active treatment followed by Modafinil 50 mg oral daily for weeks 13-24 of the active treatment period. The drug will be washed out for a 2 week period with repeat assessments to determine any withdrawal symptoms.

[figure not shown]

Figure 1: Delayed-start trial model with 1:1 randomization into an early-start arm with 10 subjects receiving Modafinil 50 mg oral daily for 24 weeks and 10 subjects randomized to a delayed-start arm receiving placebo for the 1st 12 weeks followed by Modafinil 50mg oral daily for weeks 13-24. Visits will be performed at initiation and randomization, followed by 6, 12, 18 and 24 week visits in the active phase with the final visit performed after a 2 week drug washout phase.

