8.0 Outcome Measures

8.1 Improvement in FOG

8.1.1 Motor assessments

Giladi freezing of gait questionnaire (FOG-Q): Validated questionnaire with 6 items rated 0-4 for a total of 24 points in total. We will be looking for a 10% change in this questionnaire to suggest a subjective improvement in freezing of gait over the course of the study.

UPDRS Part III motor score: Validated rating scale used to quantify the movement disorders motor examination including items for bradykinesia, tremor, rigidity and gait.

Gait and balance measures: Will evaluate for changes in steady state gait and balance measures using the assessments outlined in section 7.2 including mean and percent coefficient of variability in:

Stride length

² Self-assessment questionnaires

PI: [name], PhD

Sponsor: UAMS

- Stride width
- Stride velocity
- Step time
- Step length
- Gait cycle time
- Swing cycle percent
- Stance cycle percent
- Single support percent
- Total double support percent
- Velocity
- Cadence
- Ambulation time

8.1.2 Cognitive assessments:

The following cognitive assessments will be administered by [name] or other trained study personnel. [name] (licensed psychologist) will supervise the interpretation of these results.

Montreal cognitive assessment (MoCA): commonly used scale to screen for cognitive dysfunction in Parkinson disease patients.

Frontal assessment battery (FAB): commonly used scale to screen for frontal lobe dysfunction that can be suggestive of atypical parkinsonisms and also associated with frontal gait disorders that also have FOG.

SCOPA-cog: cognitive rating scale used in European trials to track cognitive function in Parkinson disease patients.

Stroop test: test of mental flexability and set shifting using colored words that FOG patients have been shown in some preliminary studies to have more difficulty with than PD without FOG patients.

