10.0 STATISTICAL CONSIDERATIONS

The study is a prospective repeated measures longitudinal design. The primary outcome response is the FOG-Q total score and the stride length changes, and the secondary responses are the UPDRS Part III subscale, the PDQ-39, the RBD scale, and the Epworth Sleepiness Scale. These measures will be observed at 6 time points for both study arms. A primary statistical goal is to estimate the mean response at all six time points for each group and subsequently estimate changes in the outcome measures for each study group from baseline. Additionally, it is of interest to estimate the how the study groups differ in their mean change from baseline. A two group repeated measures linear model will be employed to determine significance for within each group and then to compare among the groups. Significance will be declared at the 5% level of significance and Bonferroni methods will be used for multiple comparisons. This analysis approach will be applied to the primary and secondary responses.

The study calls for 10 subjects in both arms for a total of 20 patients. Within a study arm the linear model will have in excess of 80% power to detect a 1.75 unit difference in observed means. Based on standard deviation estimates from previous researchers in similar settings,²² the FOGQ (the primary response) has a standard deviation of 3.58. This implies that we will have power to detect a 6.265 (1.75*3.58) unit difference among time point means at the 5% level of significance. Power calculations are from 'Tables of Sample Sizes in the Analysis of Variance' published by Bratcher.²³

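### Endpoint 4.4.1.2 judges stride-length decline by a rate with no stated window, visits or contrast; over 12-week phases, a lasting symptomatic gain looks the same as slowed decline

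*Combined protocol and SAP*

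**What the plan says.** - Section 4.4.1.2, one of two primary endpoints, asks whether the drug lessens the loss of stride length. Stride length at steady state is to be plotted by arm to "determine if the rate of decline improves in subjects taking Modafinil in the early-start arm". For the other arm, after its switch to active drug, the question is "whether this rate of decline also improves in the second phase of the trial in the delayed-start arm". No window, visit set, fitted line or contrast is given.
- The next paragraph of 4.4.1 turns to other gait parameters, excluding stride length. A different change in slope at 24 weeks is taken there as "compared to the delayed start arm suggesting that Modafinil slows the progression of the gait decline".
- Section 3.3 says that "with the delayed start model we will also determine if there are any changes in the slope of decline in PD-FOG patients". The same section justifies the design mainly by recruitment and retention.
- Section 8.1.1 states: "Will evaluate for changes in steady state gait and balance measures". Steady state therefore describes the kind of walking and does not select visits.
- The Figure 1 legend in 6.2 states: "Visits will be performed at initiation and randomization, followed by 6, 12, 18 and 24 week visits in the active phase", with a last visit after washout. The 7.3 table marks gait at all six visits. The text of 7.2 lists only enrolment, 6 and 12 weeks on drug, and 2 weeks after stopping.
- Section 6.2 gives the purpose of the last visit: "The drug will be washed out for a 2 week period with repeat assessments to determine any withdrawal symptoms".
- Section 10 plans a two-arm repeated-measures linear model for the means at six time points. It also aims to "estimate the how the study groups differ in their mean change from baseline". It has no slope term.

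**The concern.** A drug that lengthens stride while it is taken and a drug that slows gait decline are different findings. A comparison of rates separates them only if the initial on-drug improvement is kept out of the rate. Section 4.4.1.2 does not say whether the last visit before active drug enters the rate, and no section ties a stride-length slowing statement to the two time points that could help: week 24, when both arms are on drug, and week 26, after washout. A report that follows the endpoint as written could describe a symptomatic effect as reduced decline.

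**Working it through.** **1. The plan's own figure.** Section 10 gives 1.75 × 3.58 = 6.265 FOG-Q points with more than 80% power. A one-way analysis of variance with 6 means, 10 per arm and a largest difference of 1.75 SD gives 83.4% (54 error df), or 82.5% (45 repeated-measures df). The figure reproduces, but it concerns FOG-Q within an arm and says nothing about stride length.

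**2. Window (inferred).** Placebo exists only in weeks 0-12 and the delayed arm's second phase is weeks 13-24. Natural visit sets are therefore weeks 0, 6, 12 and weeks 12, 18, 24.

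**3. The 12-week slope.** The least-squares weights at weeks 0, 6, 12 are -1/12, 0, +1/12, so slope = (Y12 - Y0)/12. With no change in the underlying decline:
- gains (0, d, d), (0, d/2, d) and (0, 0, d) each add d/12 per week;
- a gain seen only at the middle visit, (0, d, 0), adds 0.

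Let D be the underlying 12-week decline (assumed; the documents give no value). Apparent slowing is d/D: 25%, 50% or 100% for d = 0.25D, 0.5D or D. The delayed arm's weeks 12, 18, 24 give the same result.

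**4. On-drug visits only (6 and 12, or 18 and 24).** A gain complete and stable by the first on-drug visit cancels. If only half is present by then, the slope gains (d/2)/6 = d/12, the same bias as before.

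**5. Illustration of rejection rates.** Assumptions: visit-level residual SD = 1, d in those units, no true slowing, 10 per arm, two-sided t test with 18 df. The SE of the difference in 12-week change is √(0.2 × (2 + (12 × slope SD)²)), where slope SD is the between-patient variation per week.

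| Slope SD | SE | Significant at 5%, d = 0.5 / 1 / 2 |
|---|---|---|
| 0 | √0.400 = 0.632 | 12 / 32 / 85% |
| 0.05 | √0.472 = 0.687 | 11 / 28 / 79% |
| 0.10 | √0.688 = 0.829 | 9 / 21 / 63% |

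At 2.5% (an assumed Bonferroni split over the two primary endpoints) the first row becomes 7 / 22 / 76% and the last 5 / 13 / 50%. For the delayed arm against its own first phase, the contrast Y24 - 2·Y12 + Y0 has variance 6; with n = 10 and 9 df the rates at 5% are 9 / 21 / 63%.

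**6. One line over weeks 0-24 (other gait parameters).** The weights are -1/30, -1/60, 0, 1/60, 1/30.
- Gain complete by the first on-drug visit: early arm d/30, delayed arm d/20, early minus delayed = -d/60 per week. The bias runs against a slowing claim.
- Gain building linearly over 12 weeks: d/24 in each arm, difference 0.

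With true slowing of 0.1 per week on drug, the slope difference without a gain is 0.1 - 0.05 = 0.05. At slope SD 0, power is 52%, falling to 27% and 10% for d = 1 and 2 when the gain is complete by the first on-drug visit.

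**7. Between-arm difference at week 24.** If the symptomatic effect after 24 weeks equals that after 12 weeks, it cancels. If it is still building linearly to week 24, the early arm has d and the delayed arm d/2, so the bias is d/2. With SE 0.632 (slope SD 0), d = 1 or 2 then gives significance about 12% or 32% of the time with no slowing.

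Precision: SE = √(0.2 × (2 + (24 × slope SD)²)) = 0.63, 0.83, 1.25 for slope SD 0, 0.05, 0.10. The 95% half-widths are 1.3, 1.7, 2.6. True slowing of 0.1 per week gives a difference of 2.4 - 1.2 = 1.2, with power 44%, 28%, 15%.

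**The case against.** The strongest reply is that the upward bias and the explicit slowing claim sit in different places. The bias belongs to the 12-week stride-length comparison, where less loss on drug than on placebo satisfies the endpoint's words whatever the mechanism. The slowing language belongs to other parameters at 24 weeks, where a single line is unbiased or biased the other way. Section 10 already models visit means, no per-patient slope test is prescribed, and a plot over six visits might itself reveal a step. The 12-week window is inferred, the magnitudes are assumed, and this is a 20-patient pilot.

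Much of this stands. It limits the severity and rules out two stronger readings:
- A reader might infer that a significant 12-week result would be a false positive. It would be a real treatment difference; only its reading as slowed decline fails.
- A reader might infer that the design cannot separate the two effects at all. The documents do not support that: visits at weeks 24 and 26 are scheduled, and the planned model yields between-arm changes from baseline.

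The reply does not remove the point. The endpoint is phrased as a rate of decline, 3.3 presents the slope as something the design will determine, and no section makes week 24 or 26 the basis for a statement about it.

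**Conclusion.** The point holds in this limited form, and is minor to moderate for a pilot. On the inferred 12-week reading, a symptomatic gain d that lasts to the end of the phase shifts the slope by d/12 per week and cannot be told from slowed decline. That identity needs no assumed SD. The rejection rates do: they rest on assumed residual and slope SDs and are illustrations only. Dropping the pre-drug visit helps only if the gain is complete and stable by week 6 or 18; it need not be immediate. A reader might also infer that the week-24 contrast is free of the symptomatic effect. It is free only if that effect has levelled off by 12 weeks on drug.

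**What to change.** In 4.4.1.2 and Section 10:
1. Name the visits, and report 12-week slope or mean differences as a treatment effect, not as slowed decline.
2. Base any slowing statement, for stride length and the other gait parameters, on the between-arm difference in change from baseline at week 24 from the planned model. Use week 26 as support, and report both as estimates with confidence intervals.
3. State the assumptions. Week 24: the symptomatic effect after 24 weeks on drug equals that after 12, and dropout or removal for progression (6.6, 7.4) does not differ by arm in a way that distorts the contrast. Week 26: equal withdrawal and carry-over effects after 24 and 12 weeks of exposure.
4. Reconcile the gait assessment times in the text of 7.2 with the 7.3 table and the Figure 1 legend. Taken literally, 7.2 omits week 24 in the early arm.

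The cost is wording: the 7.3 schedule already has the visits, and the model is planned. The downside is low precision with 10 per arm, so a slowing claim is unlikely. Week 26 is also fragile: on the same assumptions, unequal withdrawal of 0.5 or 1 residual SD with no slowing gives significance 12% or 32% of the time at slope SD 0, and 7% or 11% at 0.10.

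### The second part of the stride-length co-primary compares the delayed-start arm with its own placebo phase, so a change shared by both arms between phases is mixed with the drug effect

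*Combined protocol and SAP*

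**What the plan says.** Section 10.0 gives stride length primary status: "The primary outcome response is the FOG-Q total score and the stride length changes". Section 4.4.1.2 sets out its two parts. The first asks whether decline improves in early-start patients on modafinil. The second asks "whether this rate of decline also improves in the second phase of the trial in the delayed-start arm".

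Under Sections 4.0 and 6.2, the delayed-start arm takes placebo for 12 weeks and then modafinil for weeks 13-24, while the early-start arm takes modafinil throughout. The schedule in Section 7.3 measures gait in both arms at all six visits.

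On analysis, Section 10.0 says: "A two group repeated measures linear model will be employed to determine significance for within each group and then to compare among the groups". The between-group quantity it names is to "estimate the how the study groups differ in their mean change from baseline". A between-arm comparison of slope change at 24 weeks is stated in Section 4.4.1 only for gait parameters other than stride length.

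Section 3.3 explains the choice of design partly by recruitment and retention, given that "all subjects know that at least during 3 months of the trial they will all be receiving active drug".

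**The concern.** In the delayed-start arm, phase 1 is placebo and phase 2 is modafinil, without exception. A before-and-after comparison there cannot tell a drug effect from anything else that differs between the two 12-week periods. Two candidates are a change in expectation around week 12 and a placebo or practice gain on the walkway soon after Visit 1. The first would make an inert drug look effective, and the second would hide an effective one.

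The early-start arm does not change treatment at week 12 and is measured at the same visits, so its change between phases shows what is shared as long as any drug benefit to slope is constant. The stated criterion does not use it. What weeks 13-24 lack is a concurrent placebo group, not a concurrently observed group.

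At stake is how the result is read. The word 'also' in the criterion invites the reader to treat the second phase as replication of the first, although it lacks the first's randomised control.

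**Working it through.** **The plan's own figure.** Section 10.0 claims over 80% power within an arm for a difference of 1.75 SD among time-point means. With 6 time points, n = 10 and least favourable means, λ = 10 × 1.75² / 2 = 15.3 on 5 and 54 df, which gives 83.4% power. Also 1.75 × 3.58 = 6.265. The figure reproduces, but it concerns FOG-Q means within an arm. It gives no SD, slope or power for stride length.

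**Assumptions.** 10 per arm, two-sided tests, changes in units of the visit-to-visit residual SD (σ = 1), stride length at weeks 0, 12 and 24. The random-slope SD τ is 0, 0.5 or 1 per 12 weeks.

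**What each comparison estimates.** Let s be the underlying slope per 12 weeks, b a constant drug benefit to the slope, and g the shared phase 2 minus phase 1 change. Taking phase 1 as reference:

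- Delayed-start: s, then s + b + g. Change = b + g.
- Early-start: s + b, then s + b + g. Change = g.
- Randomised weeks 0-12 difference: (s + b) − s = b.

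The before-and-after criterion estimates b + g; the randomised contrast estimates b.

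**False positives with no drug effect.** Per patient, c = (y24 − y12) − (y12 − y0) = y24 − 2·y12 + y0. Its variance is 1 + 4 + 1 = 6, and random slopes cancel. A shared step g after week 12 has standardised size g/√6. The test is a one-sample t with n = 10 and noncentrality (g/√6)·√10.

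| Shared step (residual SD) | g/√6 | Rejects at 5% | Rejects at 2.5% |
|---|---|---|---|
| 0 | 0 | 5.0% | 2.5% |
| 0.5 | 0.204 | 8.9% | 4.9% |
| 1.0 | 0.408 | 21.2% | 13.1% |
| 1.5 | 0.612 | 40.9% | 28.5% |
| 2.0 | 0.816 | 63.4% | 49.2% |

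The 2.5% column assumes Bonferroni over the two co-primaries; the plan does not define the family. A simulation using all five visits from week 0 to week 24 agrees in pattern: a shared slope change of about 0.67 SD (in SDs of per-patient slope change) gave 46% rejections at 5%.

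**The opposite direction.** With a true slowing of 2 SD per 12 weeks and no shared change, before-and-after power is 63.4%. A lasting shared gain of 1 SD after Visit 1 adds 1 to y12 and to y24, so c shifts by 1 − 2 = −1. The mean of c falls from 2 to 1 and power to 21.2%.

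**Both parts together.** With no drug effect, the randomised weeks 0-12 contrast is significant in favour of modafinil in 5%/2 = 2.5% of trials. A favourable result on both parts cannot exceed that. Simulated joint rates at τ = 0 are 1.3%, 1.8% and 2.5% for steps of 0.5, 1 and 2 SD.

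**Power of the randomised contrast.** The per-patient variance of y12 − y0 is 2 + τ². For a 2 SD slowing the standardised effect is 2/√(2 + τ²) = 1.41, 1.33 and 1.15 at τ = 0, 0.5 and 1. A two-sample t on 18 df then has power 84.8%, 80.5% and 68.5%, above the 63.4% of the before-and-after test.

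**Would subtracting the early arm's slope change serve instead?** With D and E for the arms and 1 and 2 for the phases, (D2 − D1) − (E2 − E1) = (E1 − D1) − (E2 − D2). Both arms take modafinil in phase 2, so under constant slowing the last bracket has mean zero. The contrast is the phase 1 result plus noise. Its correlation with phase 1 is 3/√(6(2 + τ²)) = 0.87, 0.82 and 0.71, and its power at a 2 SD slowing is 41%. For a purely symptomatic gain d that appears and holds, the delayed arm's c shifts by +d and the early arm's by d − 2d = −d, so the contrast returns 2d.

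**The case against.** **The uncontrolled test is a reading of the text.** Section 4.4.1.2 speaks of plotting stride length in both arms, Section 10.0 fits one two-group model, and no paired test is written down. This stands in part: a between-arm phase contrast is unstated rather than excluded. But the criterion asks about improvement within the delayed-start arm, Section 10.0 provides within-group significance tests, and the only between-group quantity it names is change from baseline. The natural reading is before-and-after.

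**The criterion does not stand alone.** It accompanies a first part that can be read as a randomised comparison. This stands, and it limits the harm. A reader might infer from the 9% to 63% rates that an inert drug would often be declared effective on stride length with replication. The documents do not support that, because the joint rate stays near 1% to 2.5%.

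**Shared changes are thinly supported.** Section 3.3 says patients know they will receive active drug for at least 3 months. Nothing shown says that they know it starts at week 12, and the trial is double-blind. Section 5.4 recruits partly from patients who already have routine gait assessments, which weakens a first-visit practice effect for them. This also stands: the size of any shared change is assumed. The confounding itself follows from the design and needs no such figure.

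**This is a pilot of 20 completers.** That is true, but the criterion is listed as primary and clarifying it needs no resources.

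**Conclusion.** The point holds in a limited form. As naturally read, the second part of 4.4.1.2 confounds modafinil with phase, and no section removes a shared change from the stride-length result. Bonferroni at 2.5% lowers the false-positive rates without curing them. The figures rest on 10 per arm, two-sided tests and assumed shared steps of 0.5 to 2 residual SD. The consequence is weak corroboration: a favourable second phase adds little to the randomised result, and an unfavourable one does not refute it.

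Two stronger readings are not supported. The trial does not lack a control for stride length altogether, because weeks 0-12 are randomised and placebo-controlled. Nor are weeks 13-24 unobserved in a second group; they lack a concurrent placebo, which is inherent in a delayed start. Whether a slope change reflects symptomatic gain or slower decline is a separate question, not settled here.

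**What to change.** In Section 4.4.1.2, and for stride length in Section 10.0:

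1. State that the stride-length conclusion rests on the randomised difference in weeks 0-12 slope, early-start versus delayed-start.
2. Report the delayed-start arm's phase-to-phase change as descriptive only, with no significance claim, beside the early-start arm's change over the same weeks.

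Do not present the difference between the arms' slope changes as supportive evidence. It largely re-uses the phase 1 result and doubles a purely symptomatic step.

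When making the edit, reconcile Section 7.2, whose text lists gait testing at enrollment, at 6 and 12 weeks on modafinil and 2 weeks after stopping, with the six visits in Section 7.3. The delayed arm's weeks 0-12 slope needs gait data during placebo.

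The cost is wording, with no new data, visits or patients. The small downside is that the second phase no longer counts as confirmatory replication; under the constant-slowing assumptions above, the contrast retained is the better powered one.
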